C.7. RECRUITMENT. The two Head Start organizations have agreed to support implementing the proposed project in their Head Start centers (**Support Letters**). Based on our prior experiences working with Head Start families, we anticipate ≥ 6 of 18 (30%) dyads per class will be willing to participate. Replacement classes will be randomly chosen if a selected class teacher refuses to participate. Building on lessons learned from prior studies and recommendations from Head Start administrators, we will involve Head Start family advocates to help with recruitment because they already have an established, trusting relationship with each family. The PI and project manager (PM) will provide participant recruitment training with communication scripts to family advocates to ensure consistency. Family advocates will distribute the recruitment packet (including cover letter, parental consent/child assent, & screening tool) in an envelope and explain the study to each caregiver in person. Each family will be asked to return the packet in a sealed envelope to the family advocate. For non-respondents, the family advocates will make a follow-up phone call, and then another packet will be mailed to each family. Each family will be asked to return the packet in an attached, prepaid envelope. Cash (\$5) will be provided for returning the packet. Prior to any data collection, written parental consent is required; if the child is age 5, written child assent is required. No data will be collected from preschoolers in the selected classes who do not have written consent or assent, but these preschoolers will be allowed to participate in intervention activities at their Head Start center. Both male and female preschoolers and caregivers will be recruited.

C.8. RANDOMIZATION AND BLINDING. Following baseline data collection, 6 randomly selected centers will be randomly assigned to intervention or control using a computerized random-number generator. Center directors and teachers will be informed of group assignment. There is no way to completely blind participants

Table 1. Inclusion and Exclusion Criteria

Preschoolers	Caregivers
Inclusion Criteria	
Parental written consent	Provide written consent
Understand and speak English	Read, understand, and speak English
3-5 years old	Primary adult caregiver (≥ 18 years old)
Enrolled in full-day or half-day Head Start program	Have at least weekly Internet access using a smartphone, tablet, or a computer

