Child written assent if 5 years old	Willing to use Facebook
Exclusion Criteria for both Preschoolers and Caregivers	
Medical conditions precluding dietary changes or PA	
Diagnosed conditions known to impact weight (e.g., Prader-Willi Syndrome) or taking weight-affecting medications (e.g., stimulants)	
Diagnosed developmental disabilities	Diagnosed mental health problems

to group; however, having two conditions in different centers minimizes the likelihood of cross-group contamination.¹²⁵ Interventionists and caregivers will not be informed of the study hypothesis and will be asked not to discuss the program with others. Data collectors and interviewers will be blinded to the randomization.

C.9. STRATEGIES TO ENHANCE ATTENDANCE AND RETENTION. The research team has demonstrated the ability to successfully recruit and retain participants.^{38,106} Retention strategies include: **1)** keeping up-to-date lists of center and participant contacts; **2)** mailing thank-you cards to boost achievement following each step; **3)** using incentives to compensate for transportation and daycare cost in data collection (\$40 at baseline and \$50 post-intervention); and **4)** sending reminders via telephone calls, text messages, or emails to caregivers who have not completed data collection, weekly tasks, or logged-on to the study's Facebook group for a week.

C.10. INTERVENTION. Rationale for the intervention duration is that 16 weeks provides a reasonable period for behavior habit formation⁴⁸ and is feasible for Head Start calenders.^{130,131} Additionally, we incorporated feedback from our 10-week prior study indicating that increasing the intervention duration would be helpful.

C.10.1. Caregiver Component. Facebook-based program including 4 habit-formation tasks/wk. (Table 2):

A Facebook study site was developed in our prior study³⁸ and will be installed on each intervention caregiver's smartphone, tablet, or computer. All caregivers will be connected via a private Facebook group. *We anticipate >80% will be Facebook users and >90% will have a smartphone with Internet access based*

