Skill training	20 min. Wed.	Improve fundamental movement skill	
 Use animal movements to teach fundamental movement skills: balance (e.g., balance on one foot, walk on a line), locomotor (e.g., running, hopping), and ball skills (e.g., kicking, throwing).
Fun physical activity	20 min. Thur.	Increase physical activity	
 Use fun activity games adapted from the CATCH early childhood activity box¹³⁸ and Eat Well Play Hard¹³⁹ to practice the movement skills covered on Wednesday. Reflect on the benefits of participating in physical activity.

* A nurse expert in child development, a pediatric nurse practitioner, and a Head Start dietitian reviewed and approved the curriculum.

C.11. CONTROL. Control group will receive usual Head Start activities during intervention period. After post-intervention data collection, each control caregiver will receive all intervention supplies and a mini program including a face-to-face caregiver meeting and 1-week preschooler program. The caregiver meeting will cover contents on alternative cooking ingredients, food labels, and portion sizes.

C.12. TRAINING. To insure intervention fidelity and high quality data, the PI, Co-Is ([name] & [name]), and PM will conduct an initial training on study protocol for the whole research team. MSU Extension health educators will receive additional training on the preschooler curriculum. The statistician, Dr. [name], and Co-I (Dr. [name]) will also train the PM as the data manager and Facebook moderator, respectively. Training manuals will be provided to all research staff.

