C.13. INTERVENTION FIDELITY MONITORING & EVALUATION. The PM will monitor the Facebook group daily to record task-completion rates and caregivers' site visits, respond to caregivers' questions and postings, and review records and posted content to ensure proper posting and functionality. Extension health educators will record caregiver meeting attendance and activities, as well as each preschooler's attendance, punctuality, participation, and activities offered for the day in a daily activity log. The PI will communicate with Extension health educators weekly to review objectives, attendance, and intervention delivery dose, and discuss issues and solutions. Head Start teachers will complete an evaluation survey on preschooler program, and caregivers will complete an evaluation survey on caregiver program and preschooler letters (**Appendix A**). Two process evaluators will observe 6 randomly sampled sessions (2/center; 1 session from Extension health educator and 1 session from teacher) to evaluate preschooler curriculum implementation and activity engagement. At post-intervention, individual interviews (**Appendix A**) with 10 randomly selected caregivers will be conducted with the PM and PI to obtain in-depth evaluation of the intervention and future suggestions for improvement.

C.14. DATA COLLECTION & OUTCOME MEASURES (Table 5, Appendix A). All outcomes will be assessed at baseline and post-intervention. Height and weight will be measured in a private room in Head Start centers. To improve compliance with wearing accelerometers, an auto text-message reminder will be sent to caregivers every morning at 7AM via the *REDCap* web application maintained by MSU CTSI-BRIC (**Support Letter**). The 24-hour dietary recall will be administered by 4 trained interviewers via telephone¹⁴⁰ on 2 weekdays and 1 weekend day,^{141,142} using the Nutrition Data System for Research (NDSR) software developed by the Nutrition Coordinating Center,¹⁴³ University of Minnesota. Trained interviewers will also observe the snacks and lunch offered at Head Start centers. Drs. [name] & [name], who have completed the 2-day training on NDSR, will assess and assure diet data quality. The Environment and Policy Evaluation and Observation-Self-Report (EPAO-SR)¹⁴⁴ will be completed by each center supervisor and two teachers on a single day to assess each

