Head Start center environment, including the physical environment, provisions, practices, policies, training, and education. All other surveys will be completed by caregivers online via REDCap web application. Caregivers will be informed of online surveys via text-message or email. Data collectors and interviewers (blinded to group assignment) will be available by phone or in-person to answer questions.

Table 5. Study Measures

Concept	Measure and Description	# Items	Time	Reliability/Validity
Preschoolers (Aim 1)				
MVPA (min/day)	7-day ActiGraph GT3X-plus accelerometer ¹⁴⁵ Cut-points: sedentary activity (<37 counts/15 s), light (38–419), moderate (420–841), & vigorous (≥842) ^{146,147}	7-day	5 min	Reliability = 0.69–0.84 ¹⁴⁸ $r = 0.66$ with observational system ¹⁴⁵
Diet quality (e.g., fruit/vegetable, fiber, sugar/fat)	Intake at Head Start center: dietary observation system on snacks and lunch on two weekdays ¹⁴⁹ Intake at home: proxy-reported 24-hour dietary recall	3-day	90 min	ICC = 0.99; ¹⁴⁹ accurate rate: 95%; ¹⁵⁰ good agreement with actual energy intake ¹⁵¹
Screen Time	NHANES-Physical Activity and Physical Fitness survey ¹⁵²	2	1 min	Reliability: $r = 0.63–0.84$ ¹⁵³
Proportion of OW/O, BMI z-score	Calculated from height and weight using CDC growth charts ¹⁵⁴ Height: Child/Adult Shorr Measuring Board Stadiometer Weight: Child/Adult Seca model 874 portable electronic scale In accordance with NHANES measurement protocol ¹⁵⁵	N/A	3 min	Specificity 0.93; sensitivity 0.73 ¹⁵⁶
Caregivers (Aim 2)				
MVPA	7-day ActiGraph GT3X-plus accelerometer Cut-points: light (0–2689 counts/60 s), moderate (2690–6166), & vigorous (≥6167) ¹⁵⁷	7-day	5 min	ICC = 0.97–0.99 ¹⁵⁸ $r = 0.81$ with oxygen consumption ¹⁵⁹
Diet quality	Fruit-vegetable-fiber screener ¹⁶⁰	10	3 min	$r = 0.71$ with full Block survey ¹⁶⁰
Screen Time	NHANES-Physical Activity and Physical Fitness survey ¹⁵²	2	1 min	Reliability: $r = 0.63–0.84$ ¹⁵³
Proportion of OW/O, BMI	Calculated using (weight kg/height m^2) ¹⁶¹ Measures are similar to those used in preschoolers	N/A	3 min	Specificity 0.97; sensitivity 0.42 ¹⁶²
Knowledge	Knowledge on preschoolers' dietary intake & physical activity ¹⁶³	25	5 min	N/A
Feeding Practice Skill	Child Feeding Questionnaire ¹⁶⁴ measuring caregiver feeding practice behaviors	33	5 min	$\alpha = 0.71–0.93$ ^{38,164,165} $r = -0.26–0.53$ with child BMI ^{164–166}
Self-Efficacy	Parental self-efficacy scale ¹⁶³	20	4 min	$\alpha = 0.72–0.94$ ^{38,163}

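### Interviewers described as blinded also observe meals inside the randomized centers, which puts the post-intervention blind on child diet quality at risk

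*Combined protocol and SAP*

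**What the plan says.** C.8 makes a general claim about assessors: "Data collectors and interviewers will be blinded to the randomization". C.14 repeats it for staff who help caregivers with the online surveys: "Data collectors and interviewers (blinded to group assignment) will be available by phone or in-person to answer questions".

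Table 5 builds child diet quality from two sources:

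- At the center: "Intake at Head Start center: dietary observation system on snacks and lunch on two weekdays".
- At home: "Intake at home: proxy-reported 24-hour dietary recall".

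C.14 says who collects them. "The 24-hour dietary recall will be administered by 4 trained interviewers via telephone", on two weekdays and one weekend day. The next sentence adds: "Trained interviewers will also observe the snacks and lunch offered at Head Start centers".

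On who knows the allocation, C.8 says: "Center directors and teachers will be informed of group assignment". It concedes that participants cannot be fully blinded. It also keeps the study hypothesis from interventionists and caregivers and asks them not to talk about the program with other people. C.4 randomizes whole centers and places outcome assessment at weeks 0 and 17. Section B has teachers leading delivery, with on-site coaching, in weeks 11-16. C.12 provides an "initial training on study protocol for the whole research team".

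**The concern.** In a cluster trial, learning the arm of a center means learning the arm of every dyad in it. A person described as blinded who enters a center at week 17, among staff who know the allocation and may have just finished delivering the program, has an obvious opportunity to learn it. If that person then telephones families from the same center, the knowledge carries into the recall, a probing interview with a caregiver who also knows the arm.

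Diet quality is an Aim 1 outcome, and C.6 anticipates an effect size of 0.50 for it. It is also one of the three behaviors in the Aim 3 dyadic model. C.6 gives the study's purpose as estimating effect sizes for later research, so differential probing or coding would be carried forward in the estimate. The trial could also report an assessor blind for child diet that it did not fully have.

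**Working it through.** The plan gives no figure for blinding, so the main check sets its statements side by side.

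1. **Same staff.** C.14 assigns the recalls to four trained interviewers, then says that trained interviewers also do the meal observation. The natural reading is one pool doing both jobs. The text does not say that the same person observes a center and telephones its families, but nothing prevents it.
2. **Place and time.** The observation is on site. C.8 puts randomization after baseline data collection, so baseline visits reveal nothing. The exposure is at week 17 only.
3. **Who could reveal the arm.** Directors and teachers at all six centers know it. At the three intervention centers, teachers led the last six program weeks (11-16).
4. **Second route.** Intervention caregivers receive a cookbook and portion plates (C.10.1) and twice-weekly child letters about foods and activities (C.10.2). Control families receive the supplies only after post-intervention data collection (C.11). A truthful recall could mention these items.
5. **Protection stated.** There is the C.8 request not to discuss the program. I find no rule separating roles, no masked call list and no check for unblinding.

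**Reach.** One center holds 24 of 144 dyads: 24/144 = 16.7%, about 17%. This is how many dyads one disclosure covers. It does not measure bias.

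**Workload** (assuming that the four recall interviewers do all the observing, with one observer per class per day):

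- Observation: 24 classes × 2 weekdays = 48 class-days; 48/4 = 12 per interviewer.
- Recalls per wave: 144 × 3 = 432; 432/4 = 108 per interviewer. If two interviewers moved entirely on site, the other two would make 432/2 = 216 each.
- Cross-assignment, with two observers per center: each interviewer enters 6 × 2/4 = 3 centers and telephones families from the other three. Each center generates 24 × 3 = 72 recalls shared by two callers, so each makes 3 × 72/2 = 108. The load does not change.

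**Illustration of sensitivity, with assumed bias.** The plan's sample size reproduces closely. For d = 0.50, two-sided 5% and 80% power, n = 2(1.960 + 0.842)²/0.25 = 62.8 per arm. With the class design effect 1 + (6 − 1) × 0.01 = 1.05 this is 65.9, so 66 per arm and 132 in total against the stated 130. Power at 130 is 0.794.

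At N = 130 there are about 5.4 children per class, the design effect is 1 + 4.4 × 0.01 = 1.044, and the standard error of d is √(4 × 1.044/130) = 0.179. With no true effect and a differential bias b, the false-positive rate is Φ(b/0.179 − 1.96) + Φ(−b/0.179 − 1.96):

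| Assumed b (SD) | Share of d = 0.50 | False-positive rate |
|---|---|---|
| 0 | 0% | 5% |
| 0.1 | 20% | 9% |
| 0.2 | 40% | 20% |
| 0.3 | 60% | 39% |

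The values of b are assumptions; nothing in the documents points to one of them. The table uses an unadjusted 5% level and the plan's class-level ICC.

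**The case against.** The strongest reply is that the documents show an opportunity for unblinding, not its occurrence. C.8 does restrict talk about the program, and that covers caregivers and, insofar as they deliver sessions, teachers. Recalls run on standard dietary software, trained investigators check diet data quality, and Table 5 cites an ICC of 0.99 for the observation method. The outcome labelled primary is accelerometer MVPA, and the study is exploratory.

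Much of this stands, and it limits what can be said. A reader might infer any of the following; the text does not support them:

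- *Everyone at the center knows the arm.* C.8 names only directors and teachers.
- *Props at meals give the arm away.* Puppets, costumes and tasting belong to separate 20-minute sessions (Table 4) of a program that has ended by week 17. Nothing says that they are on view at snacks or lunch. C.12 trains the whole team on the protocol but reserves the extra curriculum training for the extension educators.
- *The program evaluation survey leaks the arm to blinded staff.* C.13 gives neither its timing relative to the recalls nor who answers questions about it.
- *The blind will fail, or the main result is compromised.* The first is a prediction that the text cannot settle. The second does not follow, because this route does not touch MVPA.

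The reply does not remove the conflict. The request not to discuss the program says nothing about assessors and cannot stop a caregiver from naming foods or materials in an honest recall. Software, quality checks and reliability figures support consistent measurement; they do not conceal the arm.

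**Conclusion.** The point holds in a limited form. Followed as written, the plan exposes a blind that it states without qualification, because interviewers work inside the randomized units and no procedure protects them there. The exposure covers child diet quality at post-intervention: the center observation directly, and the home recall wherever the same person does both jobs or a caregiver reveals the arm.

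This rests on reading C.14 as one pool of interviewers, which its wording favors but does not prove. One disclosure covers 17% of dyads. Neither the size of any resulting bias nor the chance that unblinding occurs can be derived from the documents. The change is worth making because it is cheap; the point does not cast doubt on the trial's primary outcome.

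**What to change.** **In C.14**

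- Require that at post-intervention no interviewer gives telephone recalls to dyads from a center that he or she has entered since randomization, including visits to answer survey questions in person. Cross-assigning the four interviewers does this with the recall load still at 108 each. Wholly separate telephone and on-site roles are an alternative if the workload allows.
- Issue call lists by a dyad ID that does not show the center. This matters because allocation is three to three: an interviewer who learns the arms of some centers learns something about the rest.
- Have recall interviewers and meal observers record a guess of the arm after their last assessment, and report the results.

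**In C.8**

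- Limit the blinding claim to staff for whom it holds, and describe on-site meal observation as possibly unblinded. If data collection is already complete, this qualification can still be made in the report.

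**Cost.** Protocol wording and less freedom in scheduling, with no added staff. The change does not blind the meal observers, and caregivers may still reveal their arm during a recall; the recorded guesses would help show how often.

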Our **primary objective** is to determine the preliminary efficacy of the intervention. **Methods:** We will conduct a **two-group cluster randomized controlled trial** (RCT). From the available 13 large Head Start centers, six centers will be randomly selected and then randomly assigned to the intervention (n=3) or control group (n=3, usual Head Start activities); 24 caregiver-preschooler dyads will be recruited from each center (N=144 dyads).

AIM 1: Determine the preliminary efficacy of *FirstStep2Health* vs control among preschoolers on proximal behavioral changes of ↑ moderate-to-vigorous PA (MVPA) measured by accelerometry (primary outcome), ↑ diet quality (e.g., ↑ fruits/vegetables, ↑ fiber, ↑ whole grains, ↑ total protein, ↑ dairy, ↓ sugar-sweetened beverages, ↓ total sugars/fats), and ↓ screen time (e.g., watching TV, playing video games); and distal anthropometric outcomes of ↓ proportion of OW/O and ↓ body mass index (BMI) z-score. We anticipate an overall decrease in BMI z-score in intervention preschoolers because we expect OW/O preschoolers’ BMI z-score to decrease and healthy-weight preschoolers to have no change. We focus on proximal behavioral changes as our primary outcome instead of distal anthropometric outcomes due to the brevity of this study and the need for behavioral changes to be maintained for at least a year before manifesting in changes in anthropometric outcomes.^{49,50} **AIM 2: Examine the preliminary efficacy of *FirstStep2Health* vs control among caregivers** on their ↑ MVPA measured by accelerometry, ↑ diet quality (e.g., ↑fruits/vegetables, ↑fiber), ↓ screen time, ↓ proportion of OW/O, ↓ BMI, ↑ knowledge, ↑ feeding practice skill, ↑ self-efficacy, ↑ parental support of their child, ↑ parenting practices, and ↑ home environment. **AIM 3: Compare *FirstStep2Health* vs control on the bidirectional relationship** (as demonstrated in the APIM) between preschoolers and caregivers on MVPA, diet quality, and screen time. Further, we will **validate established feasibility, acceptability, and satisfaction of the intervention using qualitative and quantitative data**.

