Get in the kitchen	Post about a healthy meal you made for your family (e.g., make a recipe of your own OR make chicken noodle soup for your family).
Make active time family time	Post about physical activity in which you helped child engage (e.g., take a walk with child, play a family activity game with child).
Leave a positive comment	Positively respond to one other person's posting (e.g., Yum! That looks like a delicious meal. Great job.).
Take a quiz	Reinforce information & strategies learned (e.g., repeatedly exposing child to novel or disliked food is an effective strategy to deal with picky eaters; true or false?).

Table 3. Caregiver Facebook-based Program Components

Component	Contents & Instructions
Front Page	Caregiver progress (# tasks completed) will be updated daily on this page.
Complete Tasks	Each Sunday morning, caregivers will receive a notification on weekly tasks and will be asked to complete tasks by midnight the following Saturday. Each Friday morning, caregivers will receive a reminder via Facebook messenger and text messaging to complete the weekly tasks. For caregivers who have not logged-on to the study's Facebook group for a week, reminders will be sent via text message, phone call, or email aligning with their preferred communication method.
Past Tasks	Past tasks can still be completed after due date because some caregivers may not be able to complete on time due to illness or other personnel events. The flexibility was highly appreciated by caregivers in the prior study.
Take A Quiz	After completing each quiz, immediate feedback will be provided (e.g., You bet! Every minute counts. The physical activity goal of 10,000 steps/day can be achieved in sessions: a morning walk, a midday walk, and an evening walk.).
Encouraging Messages	Messages on parental influence will be posted on the private Facebook group's front page every other day to encourage caregivers to take little steps at a time to help make healthy behavioral changes in the family (e.g., To the world, you're a mother, but to your child, you are the world.).
Talk to a Researcher	This will allow caregivers to send private messages to the research team via Facebook messenger if needed to obtain advice on healthy diet and PA.

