other free or affordable PA facilities) and provide caregivers a resource manual. Each caregiver will receive a binder including all intervention materials to ensure access to intervention information after intervention ends.

C.10.2. Caregiver-Preschooler Learning. Each week, preschoolers will create two letters using stickers regarding a food or activity presented in the center-based program that they liked or wanted to try at home. Letters will be sent by the PM privately to each caregiver via Facebook messenger every Wed. and Fri. Caregivers will be encouraged to discuss letters with their preschoolers and offer foods and activities desired by preschoolers. They will also be asked to answer two Facebook multiple-choice questions related to the letters each week by Sun. midnight (**a. What foods listed in your child's letter did you provide? b. What activities listed in your child's letter did your family try?**). Caregiver responses to the questions will be summed to indicate caregiver responses to child requests. Each preschooler's letters will be kept in his/her intervention binder with other intervention materials to present to his/her caregiver at Meeting 3. Weekly preschooler activities, with pictures or videos, will be shared with caregivers via the Facebook private group every week.

C.10.3. Center-based Preschooler Component (Table 4). Built on previous research,^{16,33,38,134-136} preschoolers will receive weekly, age-appropriate, participatory learning³⁴ co-delivered by teachers and MSU Extension health educators. Session duration will be 20 minutes because children's normal attention span is 3–5 minutes per year of age,¹³⁷ and 20 min/session is recommended for preschoolers.⁴

Table 4. Weekly Healthy Eating and PA Program at Intervention Head Start Centers			
Theme	Dose	Objectives	"Eat & Walk My ABCs" Curriculum*
Healthy eating learning	20 min. Mon.	Increase knowledge	
 Learn where food comes from, how its grown, and its nutrition. Use food cards, costumes, food handheld puppets, and role-playing games.
Taste-testing activities	20 min. Tues.	Expose to healthy foods	
 Use senses to understand the foods covered on Monday (how a food looks, smells, feels, and tastes).

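### Caregiver screen time (Aim 2) may include time spent on the study's own Facebook program in one arm only, and the plan has no means of telling the two apart.

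*Combined protocol and SAP*

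**What the plan says.** - **Outcome.** The Aim 2 list in Specific Aims marks several caregiver measures as expected to fall, among them "screen time, ↓ proportion of OW/O, ↓ BMI, ↑ knowledge" being the next expected gain. Aim 3 compares the arms on the caregiver-preschooler relationship for MVPA, diet quality and screen time.
- **Measure.** Table 5 gives the caregiver instrument as the "NHANES-Physical Activity and Physical Fitness survey", two items, one minute. C.4 sets the assessments at week 0 and week 17.
- **Delivery.** C.10.1 describes a "Facebook-based program including 4 habit-formation tasks/wk". The study site goes onto a device of every caregiver in the intervention arm: "smartphone, tablet, or computer. All caregivers will be connected via a private Facebook group". Table 3 adds encouraging posts every other day and reminders to caregivers who have not logged on for a week. C.10.1 also provides a weekly electronic flyer.
- **Letters.** Under C.10.2, "Letters will be sent by the PM privately to each caregiver via Facebook messenger every Wed. and Fri". Caregivers answer two Facebook questions about the letters each week and see shared pictures or videos in the group.
- **Control.** C.11 gives control caregivers usual activities during the intervention period, and supplies and a mini program only after the post-intervention data are collected.
- **Not stated.** Table 5, C.14 and C.15 do not say whether study Facebook use is to be counted, left out, recorded for this outcome or handled in the analysis. C.13 logs site visits, for fidelity monitoring.

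**The concern.** The intervention arm is asked, and prompted, to use a screen each week, and the trial then tests whether screen time fell in that arm. Any study use that enters the survey answers enters one arm only and works against the hypothesis. Randomization and blinded data collectors do not remove it, because receiving the treatment produces it.

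With no instruction on what to count, caregivers may also differ in how they answer. A null or adverse result could then mean that recreational screen time did not fall, or that it fell and was masked by program use. C.6 says that the trial is meant to supply effect sizes for later research. That statement is about preschooler outcomes, but a caregiver estimate reported beside them could be carried forward in the same way.

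**Working it through.** **The plan's own figure.** The only sample-size statement (C.6) concerns preschooler outcomes: N = 130 for power 0.80 at d = 0.50, alpha 0.05, class ICC 0.01. With a two-sided test, 63 per arm is 126 in total. The design effect for 6 dyads per class is 1 + (6 − 1) × 0.01 = 1.05, and 126 × 1.05 = 132.3, close to 130. The figure reproduces, and this point does not alter it. No effect size or power is given for caregiver screen time.

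**Inputs for the shift.** The protocol gives neither minutes of program use nor an SD for caregiver screen time. Both are assumed here:
- study use *u* = 30, 60 or 120 min/week;
- SD = 60, 90 or 120 min/day;
- first case: all study use is counted in the two answers, and all of it is additional to other screen use.

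**Formula.** Shift in SD units = (*u* / 7) / SD.

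Minutes per day: 30/7 = 4.3; 60/7 = 8.6; 120/7 = 17.1.

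| Study use | SD 60 | SD 90 | SD 120 |
|---|---|---|---|
| 30 min/week | 0.07 | 0.05 | 0.04 |
| 60 min/week | 0.14 | 0.10 | 0.07 |
| 120 min/week | 0.29 | 0.19 | 0.14 |

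The range is 0.04 to 0.29 SD, against the intervention.

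**Partial counting and replacement.** If a fraction *c* of screen use is captured by the items, and a fraction *s* of study use replaces other use captured at the same rate, the shift is multiplied by *c* × (1 − *s*). With *c* = 0.5 and *s* = 0.5 the multiplier is 0.25, and the range becomes 0.01 to 0.07 SD. With *c* = 0 or *s* = 1 it is zero.

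**Comparison.** The only screen-time effect in the document is d = −0.21, in preschoolers (C.2). One of the nine cells exceeds 0.21 (120 min/week with SD 60). The next largest is 0.19.

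**Aim 3.** Path coefficients depend on variances and covariances. If every intervention caregiver's answer rises by the same constant *k*, then Cov(Y + *k*, X) = Cov(Y, X), and the coefficients do not change. If counted study use U varies between caregivers, then Cov(Y + U, X) = Cov(Y, X) + Cov(U, X), and the variance of the caregiver variable changes too. Only that variation matters for Aim 3.

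**The case against.** The strongest reply is that the deciding fact cannot be seen. The wording and recall window of the two items are not in the available text. The only examples of screen time, watching TV and playing video games, stand in the preschooler aim. If the caregiver items are similar, Facebook on a phone may not be counted. This stands, and it is why the point is conditional.

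Replacement is also plausible. C.10.1 expects more than 80% of caregivers to be Facebook users, Table 1 requires willingness to use it, and section B says that the program is meant to fit daily routines. Gross study minutes are therefore not the same as added minutes. This stands too.

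The content should not be counted twice. In Table 2 the quiz and the comment are two of the four weekly tasks, and the other two are posts about a meal and an activity that take place off-screen. The upper assumption of 120 min/week has no support in the document beyond being a deliberately high value.

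Total screen time, including what the program itself induces, is a legitimate intention-to-treat outcome. That is a reason to keep it as the main analysis. It does not remove the need to know how much of it is study use.

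A reader might infer more than the text supports:
- **That study use runs past the week-17 survey.** Table 3 says "Past tasks can still be completed after due date because some caregivers may not be able to complete on time", which concerns weekly due dates. It says nothing about use after the program ends. Carry-over depends on the unstated recall window.
- **That the artefact would cancel any real benefit.** That needs the most extreme pairing of assumptions, full counting and no replacement, and the benchmark is a preschooler effect.
- **That Aim 3 is biased as a matter of course.** A uniform addition leaves its path coefficients unchanged.
- **That controls also join the group, because C.10.1 speaks of all caregivers.** The sentence follows one about intervention caregivers, within the intervention component, and C.11 gives controls no such access.

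**Conclusion.** The point holds in conditional form. The outcome, the delivery by Facebook in one arm and the absence of any rule on study use are all in the text. The bias arises to the extent that the two items capture study use and that this use does not displace other screen time. Its direction is then against the intervention, so it could hide a reduction but could not create a false claim of benefit.

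Its size is unknown. It is about 0.04 to 0.29 SD under the assumed minutes and SDs with everything counted and additional, less with partial counting or replacement, and zero if nothing is counted. Caregiver screen time is one of eleven caregiver outcomes listed under Aim 2. The primary outcome, preschooler MVPA by accelerometer, is untouched. This is a modest gap in interpretation that is cheap to close, and it is not a threat to the trial's main result.

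**What to change.** 1. Keep the two items in Table 5 and keep total caregiver screen time as the main analysis. State in Table 5 or C.14 what the items cover and their recall window.
2. Add one item, fielded at week 17, to the evaluation survey that intervention caregivers already complete (C.13). Ask for minutes per day on the study's Facebook group and messages over the same recall window, and whether that time was included in the screen-time answers. Asking control caregivers the same question would reveal the other arm's program, so it should go to the intervention arm only.
3. In C.15, pre-specify a sensitivity analysis of caregiver screen time net of counted study use, for Aim 2 and for Aim 3 where the variable is used, and report it beside the total.
4. Use the site-visit log in C.13 as a coarse check only, since it records visits and not minutes. If the week-17 surveys are already complete, the log is what remains for a rough sensitivity analysis.

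The cost is one survey item and a short addition to C.15, with no change to the intervention, the sample size or the primary analysis. The downside is that the net value rests on a single self-report item from one arm and over-corrects where study use replaced other use. The total and net results should therefore be read as a range.
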